The study is a single-blinded randomised controlled trial. Participants are older adults, aged 67 or older, receiving home help services, who are able to walk with or without walking aids, who have experienced at least one fall during the last twelve months and who have a Mini Mental State Examination of 23 or above. The intervention group receives a programme, based on the Otago Exercise Programme, lasting twelve weeks including home visits and motivational telephone calls. The control group receives usual care. The primary outcome is health-related quality of life (SF-36). Secondary outcomes are leg strength, balance, walking speed, walking habits, activities of daily living, nutritional status and falls efficacy. All measurements are performed at baseline, following intervention at three months and at six months' follow-up. Sample size, based on the primary outcome, is set to 150 participants randomised into the two arms, including an estimated 15-20% drop out. Participants are recruited from six municipalities in Norway.

Discussion:

This trial will generate new knowledge on the effects of an exercise falls prevention programme among older fallers receiving home help services. This knowledge will be useful for clinicians, for health managers in the primary health care service and for policy makers.

Trial registration: ClinicalTrials.gov. NCT02374307. First registration, 16/02/2015.

Keywords: Falls prevention, Home help services, Elderly, Quality of life, Older adults, Exercise, Balance, Preventative care

Background

Older adults and health-related quality of life

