The intervention performed is based on the OEP, including home visits and motivational phone calls [44]. Balance exercises comprise tasks in standing, walking backwards, stair-walking and rising from a chair. Strengthening exercises uses ankle weight cuffs to strengthen hip extension and abduction, knee flexion and extension and ankle plantar and dorsiflexion. The programme also includes warm-up exercises as movement of neck and shoulders. The OEP has been described in more detail previously [44]. This programme has been shown to be effective in reducing number of falls and number of injuries resulting from falls in addition to improving strength and balance, and maintaining falls efficacy in home-dwelling older adults [45].

In previous studies the OEP has been performed over a period of one year [45]. A meta-analysis by Sherrington et al. [46], looking at the effect of falls prevention programmes, recommend a dose of at least three hours of exercise weekly for six months. This weekly dose is attempted, but the duration of three months is shorter than in previous studies. Nevertheless, as in the original OEP, the same number of home visits and telephone calls will be made, and the participants will be encouraged to do a sufficient amount of exercise between home visits. The rationale for the change in duration and frequency is both theoretical and pragmatic. Participants included for this study are frail older adults who have a fall history and who receive home help services. Previous research has shown that home help receivers fall more frequently and have a higher level of fear of falling [27, 47]. Poor health, fear of falling, depression and lack of strength are barriers for older adults in order to adhere to exercise programmes [48]. The participants in this study are thus likely to have a lower level of observance compared to more independent elderly and a duration of one year might be too long. Additionally, previous research has shown that falls prevention programmes which were considered too demanding by the participants even had a negative impact on QOL [49]. On the other hand, only receiving a few visits might not provide sufficient support which in turn could limit adherence. The

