pragmatic rationale relates to the organizational structure of physiotherapy services in the primary health care. For this group of older adults an intervention of three months is within the time frame of what the physiotherapists normally can provide. Finally, previous research has shown that also falls prevention programmes with a shorter duration than six months have had a positive effect on QOL [21].

The physiotherapists visit the participants at home five times during the intervention (week 1, 2, 4, 8 and 10) for instruction and for guiding the appropriate level and progression of each exercise. This includes one additional visit compared to the first twelve weeks of the original OEP intervention [44]. Each visit will take about one hour. The first visit may take longer as initial information is given and a relationship is established. At this visit advice related to safety when performing exercises is provided to the participants, both orally and written. In between supervised sessions, participants will be encouraged to continue exercising on their own three times weekly for 30 minutes. Equipment for exercising (ankle cuff weights of 1, 1,5, 2 and 2,5 kg) is provided for each participant. The weeks between home visits, the physiotherapists call the participants to motivate them to continue exercising and to answer possible questions. As a part of the programme, the participants are also encouraged to perform at least two or more weekly walks of ≥ 30 minutes. The participants are provided with a written exercise booklet including illustrations. Following the intervention period, the participants are encouraged to keep the exercise equipment and booklets, in order to continue exercising.

The participants in the control group will receive usual care from the primary health care service. Following reassessment, the participants will have opportunity to participate in other falls prevention programmes, for example, already existing balance exercise group classes.

Education of intervention deliverers

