HRQOL is the primary outcome measured by the Short Form 36 Health Survey (SF-36) [52]. This is a generic and validated questionnaire which, translated into Norwegian, is conducted as an interview [53]. The 36 items in SF-36 are grouped into eight health status scales: physical functioning, role limitations due to physical problems and due to emotional problems, bodily pain, general health perception, vitality, social functioning and mental health [52].

Secondary outcome variables

In addition to the SF36, the EQ-5D (1990 EuroQOL EQ-5D) is reported. The EQ-5D is a generic and validated questionnaire [54-57]. It describes five dimensions of HRQOL (mobility, self-care, usual activities, pain/discomfort, anxiety/depression), each of which can take one of five responses at five levels of severity (no problems/slight problems/moderate problems/severe problems/severe problems/extreme problems).

Physical function includes measures of balance, gait speed, muscle strength as well as activities of daily living. The Bergs Balance Scale is a 14-item scale, which is applied to assess static and dynamic balance in older adults [58]. Gait speed is assessed by measuring usual walking speed over four meters [59] and muscle strength is measured by the 30 seconds sit to stand test [60]. Instrumental ADL is recorded using the Norwegian Version of the Lawton IADL scale, which is a valid and reliable measure of a person's self-reported ability to perform complex activities of daily living [61].

Physical activity is measured using the “Walking habits questionnaire”, a valid questionnaire for walking habits and physical activity for frailer older people [62]. This questionnaire assesses general behaviour of walking, regarding how often and for how long. The following questions are asked: “Do you take a daily walk?” (yes/no) or “If you do not take a daily walk how many times per week do you take a walk?” (never/almost never/1-2 days/3-4 days/ almost daily) and “How long does you walk generally last? (0-15 mins/15-30mins/30-60mins/ 1h-2h/>2h)”. Walking time in minutes per week is calculated by taking the lowest level of days multiplied by lowest level of minutes for each response alternative [62].

Nutritional status is measured using the Mini Nutritional Assessment (MNA- elderly, Société des Produits Nestlé, S.A., Vevey, Switzerland) form. The first screening part of six questions is used which includes measurement of weight and height for calculation of BMI [63-65].

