Statistical analysis is performed using SPSS or a similar statistical package. Descriptive data are reported for variables of interest. The data will be analysed following the intention to treat principle [72]. Prospective differences in primary and secondary outcomes and baseline characteristics between the intervention group and the control group will be assessed by t-tests for continuous and normal distributed variables and with non-parametric tests for categorical variables. Multiple linear regression modelling are used to control for confounding of between-group differences [73]. Hypotheses about mediating factors are tested through correlations, multiple regressions and bootstrapping methods exploring the correlations and explained variance of the chosen mediating factors and the changes in QOL [74]. Bootstrapping is a non-parametric method and is considered favourable with dichotomous variables (group 1 and 2) and small samples ($n < 250$) [74].

Discussion

The main purpose of the study is to evaluate the impact of OEP on HRQOL in older adults receiving home help services. We anticipate that the intervention described in this protocol will have a positive impact on the HRQOL. The tailored intervention will have a potential to promote evidence-based decision-making and empower older people receiving home help services to remain to a greater extent in charge of their own lives. We rely on a systematic approach, which corresponds with the guidance on developing and evaluating RCTs [75]. Only a few studies have included HRQOL when measuring the effect of a falls prevention programme, and most of these studies include it as a secondary outcome [21, 76]. Outcomes examining HRQOL are selected based on literature identifying a standard set of measurements in falls prevention programmes [77, 78]. SF-36 is chosen due to its good validity, reliability and responsiveness when assessing older adults [79]. This outcome is detailed and broad, but it might be putting a burden on the participants due to its length and sensitive questions. Nevertheless, estimating HRQOL is important to determine whether the effect of a falls prevention programme is significant enough to achieve clinical relevant changes and thus to justify the implementation.

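### As printed, the weekly walking-minutes score is 0 for every frequency answered with 0-15 mins, so a change between never walking and short walks, even daily ones, does not register in it

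*Combined protocol and SAP*

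**What the plan says.** The Abstract (Methods) names the outcome: "Secondary outcomes are leg strength, balance, walking speed, walking habits". Under Secondary outcome variables, physical activity is measured with a walking habits questionnaire, of which the protocol says: "This questionnaire assesses general behaviour of walking, regarding how often and for how long".

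- **Frequency.** A yes/no question asks about a daily walk. Those who do not walk daily choose from "never/almost never/1-2 days/3-4 days/ almost daily".
- **Duration.** The usual length of a walk is chosen from "0-15 mins/15-30mins/30-60mins/ 1h-2h/>2h".
- **Score.** Weekly minutes are "calculated by taking the lowest level of days multiplied by lowest level of minutes for each response alternative", with reference 62 cited.

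No replacement value is given for the zero at the bottom of the shortest band. No number of days is given for almost never, almost daily or daily.

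Statistical procedures sets a general rule, t-tests for continuous normal variables and "non-parametric tests for categorical variables". It does not mention the walking frequency item.

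**The concern.** The questionnaire collects two things, how often and for how long. The only derived measure the plan describes multiplies their lower limits, and one of those limits is 0. For anyone who answers 0-15 mins, the product discards the frequency answer altogether.

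This deserves a look because of who is enrolled and what they are asked to do. Study intervention says: "Participants included for this study are frail older adults who have a fall history". Short walks are plausible in such a group, and walking is part of the programme. If some participants go from not walking to short regular walks, or the reverse, the minutes score will not show it, although the answers on the form do.

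**Working it through.** **Inputs.** From Secondary outcome variables, the lower limits of the duration bands are 0, 15, 30, 60 and 120 minutes. The lower limits of the frequency answers are never = 0, 1-2 days = 1 and 3-4 days = 3. Three day values are not printed. I take daily = 7 as the plain reading, and show ranges for almost never (0 to 0.5) and almost daily (4 to 6) as assumptions. The protocol prints no walking score, so there is no figure to reproduce.

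**Formula.** Score = lowest days x lowest minutes.

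| Frequency (days used) | 0-15 mins | 15-30mins | 30-60mins | 1h-2h | >2h |
|---|---|---|---|---|---|
| never (0) | 0 | 0 | 0 | 0 | 0 |
| almost never (0 to 0.5, assumed) | 0 | 0 to 7.5 | 0 to 15 | 0 to 30 | 0 to 60 |
| 1-2 days (1) | 0 | 15 | 30 | 60 | 120 |
| 3-4 days (3) | 0 | 45 | 90 | 180 | 360 |
| almost daily (4 to 6, assumed) | 0 | 60 to 90 | 120 to 180 | 240 to 360 | 480 to 720 |
| daily (7) | 0 | 105 | 210 | 420 | 840 |

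**First column.** Every entry is 0. This does not depend on the assumed day values, because any number times 0 is 0.

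**Walking time that can lie behind those zeros.** The upper limit is highest days x 15 minutes:

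- 1-2 days: 2 x 15 = 30 minutes a week
- 3-4 days: 4 x 15 = 60 minutes a week
- daily: 7 x 15 = 105 minutes a week

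**Changes over time.**

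- Never to daily walks of up to 15 minutes: 0 to 7 x 0 = 0, so no change is recorded.
- Daily walks moving from the 15-30mins answer to the 0-15 mins answer: 7 x 15 = 105 to 0, the same recorded loss as stopping altogether.
- Never to the programme's target: Study intervention encourages participants to "perform at least two or more weekly walks of" 30 minutes or longer. Two such walks, answered 1-2 days and 30-60mins, score 1 x 30 = 30, so this change is recorded.

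**The case against.** **The rule is a conservative lower bound taken from a cited source.** This is fair. A uniform lower bound is a coherent choice, and the documents do not show whether reference 62 codes the shortest band as 0 in practice. That argues for keeping the score and confirming the coding. It does not restore the frequency information that the printed rule discards.

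**The general rule may already cover the frequency item.** Walking habits are the named outcome, and categorical variables are assigned non-parametric tests, so a comparison of frequency would be within the plan's spirit. It is not specified, however: the item is not named as an analysed variable, and the only walking measure described is the product.

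**The programme aims at longer walks, which register.** This is true, and it limits the consequence. What goes unrecorded is change between not walking and walks in the shortest band.

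**Two stronger readings are tempting, and the documents do not support them.**

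- A reader might infer that the score ranks participants wrongly, for example by placing a daily short walker below someone with a single 30-minute walk a week. The answers do not settle the true order. Daily with 0-15 mins covers 0 to 105 minutes a week, and 1-2 days with 30-60mins covers 1 x 30 = 30 to 2 x 60 = 120. These ranges overlap. Category midpoints give 7 x 7.5 = 52.5 against 1.5 x 45 = 67.5, the same order as the printed rule.
- A reader might infer that the zero should be replaced by a mid-value such as 7.5 minutes. That would mix one midpoint with lower bounds elsewhere and create new errors. Daily 5-minute walks (7 x 5 = 35 true minutes) would score 7 x 7.5 = 52.5, while two 50-minute walks (100 true minutes) would still score 30. It would also override a cited scoring rule that cannot be inspected here.

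**Conclusion.** The point holds for the derived score as printed. All frequencies combined with 0-15 mins give 0, so a change between never walking and short walks of any frequency up to daily does not register, although true time may reach 105 minutes a week. The zero column follows from the printed bands and rule alone; the 105 takes daily as seven days.

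The importance is low. One secondary outcome is affected, the raw answers keep the information, and the SF-36 primary outcome and the sample size are untouched. The share of participants who will answer 0-15 mins is not given, so the loss of sensitivity cannot be sized. A reader might infer that the comparison between arms is biased. Nothing in the documents shows that, since the same rule applies to both groups. The conclusion also depends on the printed rule being the one applied: if reference 62 gives the shortest band a non-zero value, the protocol only needs to say so.

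**What to change.** Keep the printed minutes score and add a few lines to the analysis plan before analysis:

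> Weekly walking minutes are reported as a lower bound. The groups are also compared at three and six months on the ordered walking frequency item (never < almost never < 1-2 days < 3-4 days < almost daily < daily) with a rank-sum test.

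The same text should give the day values used for almost never, almost daily and daily, and should confirm the coding of 0-15 mins against reference 62. Without stated values, the coding of those answers is left to be chosen after the data are seen.

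The frequency comparison needs no assumed minutes, uses answers already collected and fits the existing rule for categorical variables. It does not separate short from long walks at the same frequency, so it belongs beside the minutes score and does not replace it. The cost is one extra comparison at each of two follow-ups on a secondary outcome. No form changes.

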Workshops and meetings will be held to inform the physiotherapists participating in the project. Before starting recruitment, one full day workshop on falls prevention and OEP is held for all therapists. Following start-up of recruitment and until the end of the project one workshop will be held approximately every fourth months. These last half a day and include one lecture on a topic concerning older people and time for discussion on the development of the project. Additional to the workshops, the researcher will have monthly meetings with the physiotherapists in the different municipalities. In order to make sure that the intervention is performed as intended, a fidelity checklist based on the OEP-manual has been developed. The physiotherapists use the checklist when conducting the home visits and phone calls.

Outcome measures

Following recruitment participants are assessed before they are randomised. Assessors are blinded to the participants' group assignment. The time window between baseline assessment and start of intervention is aimed to be within two weeks, and the same time window for assessments due at three and six months. Measurements and their order are selected to avoid physical and mental fatigue of the participants. Outcome measures that are employed have established reliability and validity, as recommended by the CONSORT group [50]. In addition to improving measurement quality and outcomes, it enables direct comparisons with other studies that investigate HRQOL and can possibly contribute to meta-analyses.

At baseline the Mini Mental State Examination (MMSE), a measurement of "Global cognitive function", is performed and is used as exclusion criteria. The maximum score is 30. A score below 23 indicates cognitive impairment and these participants are excluded [51]. Sociodemographic characteristics, like age and education, are also assessed at baseline. Primary and secondary outcome measures will be performed at baseline, at three months and at six months' follow-up.

Primary outcome variable

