Falls efficacy is assessed using the Falls Efficacy Scale International (FES-I). This scale has shown good reliability and validity assessing concerns about falling in older adults, and is recommended for clinical trials and practise [66, 67]. It is a self-reported questionnaire, containing 16 items on different activities of daily living. Level of concern is measured on a four-point scale ranging from 1, which is not at all concerned, to 4 which is very concerned [68].

Adherence to the programme is documented through an activity diary completed by the participants and a form checked by the physiotherapists during home visits and calls. Additionally, the participants have a falls calendar where they report adverse events. Adverse events are registered in the following four categories: falls, cardiovascular events, musculoskeletal injuries and health care utilization and will be documented as “due to the intervention” or “not due to the intervention” [69].

Sample size estimation

The sample size is estimated from the primary outcome, HRQOL (SF-36). A treatment difference of 10 points between the two groups in one of the domains in SF-36 is regarded to be of statistical and clinical significance. The associated standard deviation is assumed to be around 20 points. This implies a moderate effect size [70], which can be expected as previous OEP studies have shown substantial effects on physical outcomes [45]. Moreover, a similar Norwegian study, which included older adults performing exercise following discharge from hospital, estimated the required sample size identically [71]. Given a power of 80% and level $\alpha=0.05$, we aim at including 150 participants, allowing for a 15-20% dropout, to detect a difference of 10 points between groups (see Figure 1).

Statistical procedures

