Eligibility criteria	10	Inclusion and exclusion criteria for participants. If applicable, eligibility criteria for study centres and individuals who will perform the interventions (eg, surgeons, psychotherapists)	6
Interventions	11a	Interventions for each group with sufficient detail to allow replication, including how and when they will be administered	7-8
	11b	Criteria for discontinuing or modifying allocated interventions for a given trial participant (eg, drug dose change in response to harms, participant request, or improving/worsening disease)	
	11c	Strategies to improve adherence to intervention protocols, and any procedures for monitoring adherence (eg, drug tablet return, laboratory tests)	8, 10
	11d	Relevant concomitant care and interventions that are permitted or prohibited during the trial	6
Outcomes	12	Primary, secondary, and other outcomes, including the specific measurement variable (eg, systolic blood pressure), analysis metric (eg, change from baseline, final value, time to event), method of aggregation (eg, median, proportion), and time point for each outcome. Explanation of the clinical relevance of chosen efficacy and harm outcomes is strongly recommended	8-10
Participant timeline	13	Time schedule of enrolment, interventions (including any run-ins and washouts), assessments, and visits for participants. A schematic diagram is highly recommended (see Figure)	6-7, 9, Figure 1

Sample size	14	Estimated number of participants needed to achieve study objectives and how it was determined, including clinical and statistical assumptions supporting any sample size calculations	10
Recruitment	15	Strategies for achieving adequate participant enrolment to reach target sample size	6

Methods: Assignment of interventions (for controlled trials)

Allocation:

Sequence generation	16a	Method of generating the allocation sequence (eg, computer-generated random numbers), and list of any factors for stratification. To reduce predictability of a random sequence, details of any planned restriction (eg, blocking) should be provided in a separate document that is unavailable to those who enrol participants or assign interventions	6-7
Allocation concealment mechanism	16b	Mechanism of implementing the allocation sequence (eg, central telephone; sequentially numbered, opaque, sealed envelopes), describing any steps to conceal the sequence until interventions are assigned	6-7,

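### The plan names SF-36 as primary but no scale, summary score or visit, and no multiplicity rule, so alpha 0.05 and 80% power attach to no identified comparison

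*Combined protocol and SAP*

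**What the plan says.** - **Primary outcome variable** (and the Abstract): HRQOL measured by SF-36 is the primary outcome. The section adds: "The 36 items in SF-36 are grouped into eight health status scales". It lists the eight and singles out none. No total score and no physical or mental summary score is mentioned.
- **Outcome measures**: "Primary and secondary outcome measures will be performed at baseline, at three months and at six months' follow-up". Neither follow-up visit is called primary here, in the Abstract or under Study design.
- **Sample size estimation**: a "difference of 10 points between the two groups in one of the domains in SF-36 is regarded to be of statistical and clinical significance". The SD is taken as about 20 points, power as 80%, alpha as 0.05, and the target as 150 participants allowing for 15-20% dropout. Domain and visit are left open.
- **Statistical procedures**: "Prospective differences in primary and secondary outcomes and baseline characteristics between the intervention group and the control group will be assessed by t-tests", with non-parametric tests for categorical variables and regression to adjust for confounding. The section gives no order of testing, no multiplicity adjustment and no criterion for success.
- **SPIRIT checklist, item 12**: the item asks for "Primary, secondary, and other outcomes, including the specific measurement variable", and for the time point of each outcome. The checklist refers the reader to the outcome pages, but those do not identify a primary scale or visit.

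**The concern.** A 5% error rate and 80% power describe one comparison fixed in advance. This plan has up to 8 scales × 2 visits = 16 between-group comparisons that could each be called the primary result, and nothing in it rules out basing the HRQOL conclusion on whichever reaches p<0.05. A reader of the final report could not then tell a planned positive result from the best of 16. The Discussion expects a positive effect and offers the results to managers and policy makers, so the main conclusion is at stake. The choice cannot be made credibly once outcomes by arm have been seen.

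**Working it through.** **Inputs from the protocol.** Difference 10 points, SD 20 (so d = 10/20 = 0.5), alpha 0.05, power 80%, 1:1 allocation, N = 150 (75 per arm), dropout 15-20%, eight scales, two follow-up visits.

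**Assumptions.** Tests are two-sided; the protocol does not say, but two-sided reproduces its N, while one-sided would need only 50 per arm. Each test uses 0.05, the only level given. All scales share one pairwise correlation r, varied from 0 to 0.8, and the correlation over time is 0.6; the documents give neither. SD 20 applies to every scale wherever several scales are considered together.

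**1. The plan's own figure.** n per arm = 2(1.96 + 0.84)²/0.5² ≈ 63, or 126 in total. Inflated for dropout: 126/0.85 = 148.2, so 149; 126/0.80 = 157.5, so 158. The stated 150 is therefore right for one comparison at 15% dropout. With 75 × 0.85 = 63.75 completers per arm, t-test power is 80.0%; with 75 × 0.80 = 60 it is 77.5%.

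**2. Smallest significant difference.** t(0.975) × 20 × √(2/n):
- n = 63.75: 1.979 × 3.542 = 7.0 points
- n = 60: 1.980 × 3.651 = 7.2 points

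A test at 0.05 is thus passed well short of 10 points.

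**3. Chance of at least one p<0.05 with no effect on any scale.** With independent tests at one visit this is 1 − 0.95⁸ = 33.7%. With correlation, from 400,000 simulated multivariate normal vectors:

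| r between scales | 8 scales, one visit | both visits | benefit only, one visit | benefit only, both visits |
|---|---|---|---|---|
| 0 | 33.7% | 52.0% | 18.4% | 30.1% |
| 0.3 | 30.0% | 47.0% | 15.2% | 24.5% |
| 0.5 | 25.0% | 39.9% | 12.6% | 20.3% |
| 0.7 | 19.2% | 31.2% | 9.6% | 15.7% |
| 0.8 | 15.7% | 26.0% | 7.9% | 13.0% |

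A single test has 5%, or 2.5% in the direction of benefit.

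**4. If an observed 10 points were required instead.** At 15% dropout the threshold is z = 10/3.542 = 2.82. The two-sided error over the same range of r is 1.9-3.8% at one visit and 3.6-7.0% over both. At 20% dropout (z = 10/3.651 = 2.74) the two-visit figure rises to at most about 9%.

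**5. If all eight scales at one visit were primary.** The Bonferroni level is 0.05/8 = 0.00625. Power for a given scale with N = 150 is 52% at 15% dropout and 48% at 20%. Power of 80% needs 104.2, so 105, completers per arm: 210/0.85 = 247.1 and 210/0.80 = 262.5, or 248 to 264 randomised in equal arms. With Holm, power to detect at least one truly affected scale (20,000 simulated trials; r = 0.7 to 0.5; 60 to 64 per arm) is about 68-76% if three scales shift by 10 points and 80-90% if all eight do. The number of affected scales is illustrative.

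**The case against.** The strongest reply is that the plan never adopts an any-scale, any-visit rule. It ties 10 points to both statistical and clinical significance, and the Discussion asks whether effects are clinically relevant. Read as a success rule, 10 points would hold the error to about 2-4% at one visit and 4-7% over both at 15% dropout (step 4), not far from nominal. But the sentence sits in the sample-size section and sets the difference to be detected; no section makes it a condition for a positive result. The inflation does depend on the any-p<0.05 reading, and the plan leaves that reading open.

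Several further points stand in part:
- The 34% and 52% figures need uncorrelated scales, which is implausible for one questionnaire. At r of 0.5 to 0.8 the figures are 16-25% and 26-40%, still far above 5%.
- The plan does not say that each visit will be tested separately. The one-visit figures do not depend on that.
- If the target is at least one affected scale, power can still reach 80-90% under Holm. The 248-264 figure applies only to 80% power for any given scale, which the protocol does not ask for.
- The reference to physical effects in earlier studies justifies the effect size; it does not select a scale.
- The primary aim is worded as exploring effects. The fixed alpha and power and the intended use in decisions point to a confirmatory reading.

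**Conclusion.** The concern holds. The documents do not identify the comparison to which alpha 0.05, 80% power and N = 150 belong. The sample size is not wrong for one scale at one visit; that scale and visit are missing. If any p<0.05 may support the claim, the false-positive chance is 16-34% at one visit and 26-52% over both, and in the direction of benefit 8-18% and 13-30% against 2.5%. These figures rest on two-sided tests at 0.05 and on assumed correlations, but the inflation is large at every correlation tried. The common SD of 20 matters only for the 10-point error rates and the all-eight power figures. This must be fixed, because it decides what the trial can conclude on its primary outcome.

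**What to change.** Before any outcome data are examined by arm:

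1. Name one SF-36 scale at one visit as primary. Physical functioning at three months, the end of the intervention, is one example that fits the effect-size rationale; the choice is the sponsor's. A summary score is possible but needs its own difference and SD, because 10 and 20 points are given for a domain.
2. Put that scale and visit into Sample size estimation in place of the unnamed domain, and state two-sided alpha 0.05 in Statistical procedures.
3. Make the other seven scales at that visit, and all eight at the other visit, secondary. Test them only if the primary is significant, by Holm or in a stated fixed order.

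This costs wording only: no extra participants or data, and N = 150 stays. The downside is that a positive result on another scale or visit becomes supportive.

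If all eight scales are to be primary, test them by Holm at one named visit and restate the power at the adjusted level, both for a given scale and for at least one. Either 248-264 participants are randomised for 80% power per scale, or the lower power (about 48-52% per scale at the Bonferroni level) is accepted and stated.
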